8.2 Serious adverse events

A serious adverse event (SAE) is one that at any dose:

- Results in death
- Is life-threatening (the term life-threatening refers to an event in which the subject was at risk of death at the time of event and not to an event which hypothetically might have caused death if it was more severe)
- Requires subject hospitalization or prolongation of existing hospitalization
- Results in persistent or significant disability/ incapacity

Examples of SAEs that do not need to be reported:

- Medical or surgical procedures (i.e. endoscopy, appendectomy); the condition that leads to the procedure may be an AE
- Situations where an untoward medical occurrence did not occur (social and/or convenience admission to the hospital)
- Anticipated day-to-day fluctuations of pre-existing disease(s) or condition(s) present or detected at the start of the study that do not worsen
- The disease/disorder being studied, or expected progression, signs, or symptoms of the disease/disorder being studied, unless more severe than expected for the subject's condition
- A hospitalization which was planned before the patient consented for study participation and where admission did not take longer than anticipated

Any SAE that occurs outside the SAE detection period (after the 30-day period) considered to be reasonably related to the investigational treatment or study participation have to be documented and reported.

This must be done within 24 hours of the initial observation of the event. The principal investigator will decide if these events are related to the protocol treatment (i.e. unrelated, likely related, and not assessable) and the decision will be recorded on the Serious Adverse Event form, if necessary with the reasoning of the principal investigator. The investigator is obligated to assess the relationship between investigational product and the occurrence of each AE/SAE. A “reasonable possibility” is meant to convey that there are facts/evidence or arguments to suggest a causal relationship, rather than a relationship cannot be ruled out. The investigator will use clinical judgement to determine the relationships. Alternative causes, such as natural history of the underlying diseases, concomitant therapy, other risk factors, and the temporal relationship of the event to the investigational treatment will be considered and investigated.

8.3 Expectedness

An ‘unexpected’ adverse event is one the nature or severity of which is not consistent with the known common side effects after radiation therapy according to the CTCAE criteria. Furthermore, reports which add significant information on specificity or severity of a known adverse reaction constitute ‘unexpected’ events.

8.4 Coherency between AEs and trial treatment

The investigator will evaluate each AE that occurred after administration of investigational medicinal product regarding the coherency with the administration of the investigational medicinal product possibly:

Related	There is a reasonable possibility that the event may have been caused by the trial treatment. A certain event has a strong temporal relationship and an alternative cause is unlikely
Probable	An AE that has a reasonable possibility that the event is likely to have been caused by the trial treatment. The AE has a timely relationship and follows a known pattern of response, but a potential alternative cause may be present.
Possible	An AE that has a reasonable possibility that the event may have been caused by the trial treatment. The AE has a timely relationship to the

trial treatment; however, the pattern of response is untypical, and an alternative cause seems more likely, or there is significant uncertainty about the cause of the event

Unlikely	Only a remote connection exists between the trial treatment and the reported adverse event. Other conditions including concurrent illness, progression or expression of the disease state or reaction of the concomitant medication appear to explain the reported adverse event
Not related	An AE that does not follow a reasonable temporal sequence related to the trial treatment and is likely to have been produced by the subject's clinical state, other modes of therapy or other known etiology

8.5 Outcome of AEs

The outcome of an AE at the time of the last observation will be classified as:

Recovered/resolved:	all signs and symptoms of an AE disappeared without any sequels at the time of the last interrogation
Recovering/resolving:	the intensity of signs and symptoms has been diminishing and/ or their clinical pattern has been changing up to the time of the last interrogation in a way typical for its resolution
Not recovered/not resolved	signs and symptoms of an AE are mostly unchanged at the time of the last interrogation
Recovered/resolved with sequel	actual signs and symptoms of an AE disappeared but there are sequels related to the AE
Fatal	resulting in death. If there are more than one adverse event only the adverse event leading to death (possibly related) will be characterized as 'fatal'
Unknown	the outcome is unknown or implausible and the information cannot be supplemented or verified

9 Quality assurance

9.1 Central review of treatment plans

To ensure consistent quality of the treatment plans a central review of the first three treatment plans in the control arm and of every treatment plan in the experimental arm will be performed prior to first irradiation. Data will be exchanged using the HIRO research data base.

The plans will be assessed by the coordinating investigators of the participating centers.

At least the following criteria will be evaluated:

- definition of target volumes
- definition of OARs
- dose prescription
- target coverage for CTV and PTV
- dose constraints for OARs
- beam arrangement

9.2 Dummy run

The Dummy Run will ensure that the contouring and treatment planning is consistent with the protocol requirements. The Dummy Run will include a submission of contouring, dose planning, and optimised re-planning for evaluation. Based on this, the study coordinators will evaluate if the centre is ready to participate and at least the above-mentioned quality criteria are met. In case of deviations from the specifications of the protocol the coordinating investigators will discuss the results and the dummy run might be repeated.

10 Documentation

10.1 Data management

As used in this protocol, the term Case Report Form (CRF) should be understood to refer to a paper form or an electronic data record or both, depending on the data collection method used at each participating center. All findings including clinical and laboratory data will be documented by the investigator or an authorized member of the study team in the

subject's medical record and in the CRF. The investigator is responsible for ensuring that all sections of the CRF are completed correctly and that entries can be verified against source data.

10.2 Patient Identification Log

All patient-related data are recorded in a pseudonymized form. Each patient is uniquely identified by a patient identification number. The investigator maintains a patient identification list in which the patient identification numbers are associated with the full patient name. This list must be kept absolutely confidential and must not leave the testing center. The patient identification list must be archived for at least 30 years after the end of the study.

All clinical data entered in the HIRO database in the eCRFs, treatment plans and imaging will be sent exclusively pseudonymized.

10.3 Data Acquisition/ Case Report Forms

The data is collected, managed and processed electronically in the in-house HIRO research database. In the case of revocation of the consent, the data may continue to be used, as long as there is no request for complete deletion of the data.

It is the responsibility of the principal investigator to conduct the study in accordance with applicable legal provisions and the study protocol, and that the data is entered correctly and completely in the eCRFs.

All data collected in this study must be documented by authorized persons in the eCRFs. Access to the database must be authorized in writing by the principal (Signature Log). Only authorized persons are granted access to the database. Access authorization may not be passed to third parties.

Data in the HIRO database will be checked by programmed value ranges, validity and consistency checks. If necessary, queries may arise that are made using the HIRO database and authorized persons. Based on the queries, the study physician / study nurse can review and answer or correct the resulting discrepancies.

The eCRFs must be completed promptly and then checked by the investigator.

After completion of the study and after entry of all relevant data and clarification of the queries, the data base will be closed.

10.4 Archiving of Study Documents

The originals of all central study documents, including documentation sheets, are kept at the Study Center for at least 30 years after the final report has been prepared.

The principal investigator of the study center keeps the administrative documents (correspondence with the ethics committee, study administration, study center), the patient identification list, the signed declarations of consent, copies of the CRFs and the general study documentation (protocol, amendments) for the above-mentioned time.

Original data of the patients (medical records) must be kept for the required archiving period of the study center, but not less than 30 years.

10.5 Confidentiality

The data obtained in the course of the trial will be treated pursuant to the Federal Data Protection Law (Bundesdatenschutz- bzw. Landesdatenschutzgesetz, BDSG-neu, LDSG and the General Data Protection Regulation (DSGVO).

During the clinical trial, patients will be identified solely by means of their year of birth, and an individual identification code (Subject ID). Trial findings stored on a computer will be stored in accordance with local data protection law and will be handled in strictest confidence. For protection of these data, organizational procedures are implemented to prevent distribution of data to unauthorized persons. The appropriate regulations of local data legislation will be fulfilled in its entirety.

The subject consents in writing to relieve the investigator from his/her professional discretion in so far as to allow inspection of original data for monitoring purposes by health authorities and authorized persons (inspectors, monitors, auditors). Authorized persons (clinical monitors, auditors, inspectors) may inspect the subject-related data collected during the trial ensuring the data protection law.

The investigator will maintain a subject identification list (subject IDs with the corresponding subject names) to enable records to be identified.

Patients who did not consent to circulate their pseudonymized data will not be included into the trial.

11 Sample Size

Sample size calculation is based on the primary endpoint “cumulative incidence of contrast enhancing brain lesions (CEBL) observed within 24 months after PRT”.

Our previous analysis showed that the primary endpoint is negative binomial distributed and that an 86 % cumulative incidence CBL negative binomial event rate, p_{conv} , as well as dispersion parameter of $\Phi = 0.2597$ can be assumed in the conventional group. On the bases of additional experiments, a 60 % reduction of the probability for at least one lesion in the model-aided experimental group is assumed, corresponding to a negative binomial event rate $p_{aided} = 0.18$ when assuming the same dispersion parameter in both groups.

For a fixed sample size design, the sample size required to achieve a power of $1 - \beta$ of 80% for the one-sided negative binomial regression at a significance level of $\alpha = 0.025$ in conventional and experimental group and a randomization allocation ratio of 1 as well as the above-mentioned assumptions, amounts to $2 * 46 = 92$. It can be expected that including covariates of prognostic importance in the negative binomial regression model as defined for the confirmatory analysis (see section 13.3) will increase the power as compared to no included covariates.

As the individual results for the primary endpoint are collected within 24 months, there is a possibility of some patients not surviving the observation period, becoming lost to follow-up or withdrawing their informed consent. If a patient discontinues from the study prematurely without having a full observation time (e.g. due to death, loss to follow, or withdrawal of informed consent) but was observed for at least one year after randomization, the primary outcome variable will be set to the number of lesions observed until the last available follow-up visit. If a patient has a follow-up less than one year after randomization, the primary endpoint will be set to missing. In order to take this potential loss of information into account, a premature death rate of 8% and a drop-out rate of 10% (loss to follow or withdrawal of informed consent) after 12 months is assumed. Thus, an overall “drop-out” rate of 18% after 12 months is assumed, and therefore the total sample size required for a fixed design amounts to $n = 92 + 22 = 114$ patients (57 per group).

A group-sequential design with interim analysis allowing to prematurely stop the trial for efficacy or futility, using O’Brien-Fleming-type alpha and beta spending functions, is

performed. This will allow to prematurely declare the treatment as effective in case of a substantially large treatment effect, as well as to stop the trial in case the treatment does not prove to be effective. The interim analysis is conducted after half of the patients did reach the primary endpoint (see the detailed description of the procedure applied for the interim analysis in section 13.3 below). Additionally, the study can be stopped in the interim analysis due to futility (boundaries for interim and final analysis are given in section 13.4). These assumptions would lead to a sample size of 98 (49 per group) without consideration of drop-outs. With an assumed 18% drop-out rate 120 patients (60 per group) are needed to achieve a power of 80%.

It should be noted that the interim analysis will likely take place after the total number of 120 patients have been enrolled. While in such a case, it is not possible to reduce the total number of enrolled patients, the follow-up time of the trial might be reduced, thus allowing to save resources and costs.

Calculations were performed with R packages gscounts for sample size calculations and MASS for estimation of the dispersion parameter. R version 3.6.3 was used.

12 Statistical Analyses

12.1 Primary objective and study design

The primary endpoint of this clinical trial is the cumulative incidence of CEBLs within 24 months after PRT measured by quarterly contrast enhanced MRI of the brain.

A group-sequential design with interim analysis according to O'Brien-Fleming type alpha and beta spending decision boundaries is performed to not withhold a possible effective treatment to the control group as well as the general trial population in case of a large beneficial treatment effect, and to prevent harm for the patients in case the experimental treatment should prove to be ineffective at interim. The interim analysis is conducted after $n = 49$ patients did reach the primary endpoint within 24 months, which is half of the planned total sample size not considering dropouts or premature deaths. No sample size recalculation is performed at the interim analysis. Furthermore, descriptive statistics for progression-free-survival and overall survival will be given at the interim analysis. This design allows early stopping of the trial under control of the overall type I error rate, or,

alternatively, a stop for futility. Results of the interim analysis will be presented to the Data Safety and Monitoring Board (DSMB) who will advise the Steering Committee of the trial to either terminate or to continue the trial.

12.2 Hypothesis

To formalize the statistical approach, the following notation will be used:

p_{conv}/p_{aided} : cumulative incidence CEBL negative binomial rate within 24 months in the conventional / model-aided experimental group. The following test problem is defined:

$$H_0: p_{aided} \geq p_{conv} \quad \text{vs.} \quad H_1: p_{aided} < p_{conv},$$

which will be assessed at a one-sided significance level of 2.5 %.

12.3 Analysis

12.3.1 Analysis sets

The allocation of each patient to the different analysis populations will be defined and explained in further detail in the statistical analysis plan (SAP) prior to the analysis.

Full Analysis Set (FAS): All patients who fulfilled the inclusion and exclusion criteria and hence were included into the trial. The term “ITT-analysis” is used for an analysis applying ITT principles to all patients of the FAS.

Per Protocol Set (PP): All patients from the FAS, excluding patients with major protocol violations. During the interim analysis, deviations from the protocol will be assessed as „minor” or „major”. „Major” protocol violations will be discussed with the coordinating investigator.

Safety Set: All patients from the FAS who received at least one fraction of radiotherapy. Patients will be allocated to the treatment they actually received.

12.3.2 Confirmatory analysis of the primary endpoint

The null-hypothesis is tested with a two-level negative binomial regression model including the covariates treatment, prescribed dose, and the random factor center. An overall one-sided significance level of $\alpha = 0.025$ is applied. Confirmatory analysis of the primary endpoint will be primarily based on the FAS which is consistent with the intention-to-treat (ITT)-principle by including all patients who were randomized to one of the study

groups. If a patient discontinues from the study prematurely without having a full observation time (e.g. due to death, loss to follow, or withdrawal of informed consent) but was observed for at least one year after randomization, the primary outcome variable will be set to the number of lesions observed until the last available follow-up visit. If a patient has a follow-up less than one year after randomization, the primary endpoint will be set to missing. An evaluation of the PP and safety set is performed additionally and the results are compared with those of the ITT analysis. Additionally, multiple sensitivity analyses of the primary endpoint will be performed by applying alternative methods dealing with missing data such as:

- Complete-case analysis, which means that the primary outcome of all patients with an incomplete 24 month follow up will be set to missing and neglected for the primary analysis.
- Analysis based on the FAS. If a patient discontinues from the study prematurely without having a full observation time, missing data for the primary outcome variable will be replaced by using multiple imputation by means of fully conditional specification method (van Buuren, 2006). The variables treatment, dose, center, lesions observed until censoring, and observation time will be included in the imputation model, which will use predictive mean matching to impute missing primary outcome data.
- Analysis based on the FAS of the primary endpoint using the non-parametric van Elteren test stratified by center, where the number of CEBLs is set to infinity for all deceased patients. If a patient discontinues from the study prematurely without having a full observation time due to loss to follow-up, missing data for the primary outcome variable will be replaced by using multiple imputation by means of fully conditional specification method (van Buuren, 2006). The variables treatment, dose, center, lesions observed until censoring, and observation time will be included in the imputation model, which will use predictive mean matching to impute missing primary outcome data.

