5.1 Treatment planning

For treatment planning, patients will be immobilized using an individually manufactured head mask. Both CT as well as contrast enhanced MR-imaging will be performed for optimal target definition. CT slice thickness should be 1 mm. Treatment planning MRI should be performed with 3T not earlier than 4 weeks prior to radiotherapy. Minimum required sequences are:

- T1 MPRAGE with and without contrast enhancement, slice thickness ~ 1mm
- 3D FLAIR / dark fluid TIRM, slice thickness ~ 1mm

Treatment planning in the control arm is performed with the available treatment planning system at each participating center (e.g. Siemens Syngo TPS, Raysearch Raystation) using a fixed RBE of 1.1. Each plan should aim for a dose distribution as homogenous and as conformal as possible. The number and directions of beams are adapted to the patient anatomy. Single beam plans must be avoided whenever possible. The optimization strategy in the conventional treatment planning arm is not determined by the protocol. In principle both Single Beam Optimization/Single Field Uniform Dose or IMPT could be used. Model-based NTCP is calculated after plan approval, however, no further adjustments are to be made to the approved treatment plan.

Re-planning in the experimental arm is performed with Raysearch Raystation, a commercially available treatment planning software with CE certification as medical medical product, using identical beam directions and normal tissue constraints as the initial treatment plan. Compared to the initial treatment plan, the following optimization objectives are modified and added, respectively:

1. the optimization objectives that control the maximum dose in the target volume employ a variable, LETd-dependent model for RBE that allows us to include the RBE-variations predicted by the NTCP model
2. the periventricular volume, defined as the volume closer than 4 mm to the ventricular wall, is included into the optimization with a constraint on its Equivalent Uniform Dose (EUD) and with the variable RBE model described above. Thereby, the combined effect of the RBE variation and increased sensitivity of the periventricular volume, as predicted by the NTCP model, is included.

The effectiveness of the re-planning is verified by a second NTCP computation.

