12.4.1 Randomisation

Screened and eligible patients will be included into the trial once the study has been initiated. The patients will be randomized with the help of the web-based software randomizer.at (provided by the Institute for Medical Informatics, Statistics and Documentation; Medical University of Graz; <https://www.randomizer.at>). Block randomization stratified by center will be performed to ensure approximately equal sample sizes within the treatment groups.

13 Ethical, legal and administrative aspects

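### The confirmatory model omits initial-plan NTCP, the trial's own predictor of CEBL, at a modest cost in precision; adjusting for it is sound only if that plan is fixed independently of allocation

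*Protocol*

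**What the plan says.** **Model.** Protocol section 12.3.2, repeated in the synopsis, tests the primary hypothesis with a "two-level negative binomial regression model including the covariates treatment, prescribed dose, and the random factor center". The test is one-sided at 0.025. The imputation models in the same section use treatment, dose, center, lesions seen before censoring, and observation time. NTCP appears in none of these.

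**Allocation and eligibility.** Section 12.4.1: "Block randomization stratified by center will be performed". No other stratification factor is named. Sections 4.1 and 4.2 set no limit on tumour location, size or predicted CEBL risk.

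**NTCP.** For conventional planning, section 5.1 says: "Model-based NTCP is calculated after plan approval, however, no further adjustments are to be made to the approved treatment plan". For the experimental arm it describes re-planning that starts from an initial treatment plan, and then: "The effectiveness of the re-planning is verified by a second NTCP computation".

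**Expected role of covariates.** Section 11 expects prognostic covariates in the confirmatory model to raise power above that of the calculation without covariates.

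**The concern.** Section 11 counts on prognostic covariates, but the model offers little that could supply the gain. Apart from treatment, the only fixed covariate is prescribed dose. The two schedules in section 5 give 30 × 1.8 = 54 and 27 × 2 = 54 Gy RBE. Section 1.3 mentions 45 to 54 Gy, so some variation is possible, but little is planned.

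The trial also rests on the premise that the NTCP model predicts CEBL: section 4 says model predictions were used to size the trial, and section 5.1 builds the intervention on them. A prognostic score of this kind, taken from the initial conventional plan, is the natural adjustment variable. Without it, between-patient differences in predicted risk stay in the residual variance, and a chance imbalance between two arms of about 49 evaluable patients carries straight into the rate ratio.

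**Working it through.** **1. Inputs (protocol section 11).** Control rate: "an 86 % cumulative incidence CBL negative binomial event rate", used as a mean count of 0.86. Experimental rate 0.18. Dispersion 0.2597. One-sided alpha 0.025, power 80%, allocation 1:1. The synopsis instead sets the experimental rate at 0.6 times control; that gives about 325 per arm and does not reproduce the plan, so 0.18 is used.

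**2. Reproducing the plan's figures.** Reading 0.2597 as the size parameter (variance = μ + μ²/0.2597):

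- Variance term: 1/0.86 + 1/0.18 + 2/0.2597 = 1.16 + 5.56 + 7.70 = 14.42.
- n per arm = (1.960 + 0.842)² × 14.42 / [ln(0.86/0.18)]² = 7.849 × 14.42 / 2.446 = 46.3. The plan states 46 per arm, 92 in total.
- Group-sequential inflation 1.056 × 2 × 46.27 = 97.7. The plan states 98.
- 98/0.82 = 119.5. The plan states 120.
- Probability of at least one lesion: 1 − (0.2597/1.1197)^0.2597 = 31.6% in controls, and 12.8% in the experimental arm. The reduction of about 60% matches section 11.

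Taking 0.2597 directly as the overdispersion gives only 23 per arm, so the size reading is the one the plan used.

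**3. How much a risk covariate could address.** The design assumes a frailty variance of 1/0.2597 = 3.85. Overdispersion makes up 7.70 of 14.42, or 53% of the variance term.

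**4. Simple analytic gain.** Power at 46 per arm is Φ(1.564 × √(46/V) − 1.96). With the dispersion part multiplied by 1, 0.9, 0.75 and 0.5, V = 14.42, 13.65, 12.49 and 10.57. Power is 79.8%, 81.9%, 85.1% and 90.4%. These shares are assumptions; the documents give no figure.

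**5. Simulated gain.** 49 per arm, likelihood-ratio test, one-sided 0.025, log-normal score times gamma frailty, no center effect. The first series has 2,000 trials per row:

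| Assumed share explained | Power unadjusted | Power adjusted | Null unadjusted | Null adjusted |
|---|---|---|---|---|
| 0% | 82.1% | 82.3% | 3.2% | 3.1% |
| 10% | 85.7% | 88.1% | 3.6% | 3.1% |
| 25% | 89.4% | 92.8% | 3.5% | 2.1% |
| 50% | 90.7% | 96.1% | 4.4% | 3.0% |

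The gains are 0.2, 2.4, 3.4 and 5.4 points. Unadjusted power also rises down the table, because part of the gamma frailty is replaced by a log-normal score; the difference within each row is the relevant figure.

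The second series holds the control probability of at least one lesion at 31.6% (500 trials per row, simulation error about 2 points):

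| Rate ratio per SD of score | Power unadjusted | Power adjusted |
|---|---|---|
| 1.0 | 80.8% | 80.6% |
| 1.65 | 78.8% | 80.8% |
| 2.2 | 80.2% | 85.8% |
| 3.0 | 83.0% | 91.2% |

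The last row is the 8-point gain. For the same rows, the analytic n per arm falls from 46.3 to 45.5, 44.0 and 41.2.

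**6. Chance imbalance.** The difference in mean standardised score between arms of 49 has SD √(2/49) = 0.20. A one-SD imbalance moves the expected rate ratio by a factor of about 1.11, 1.18 or 1.25 at rate ratios per SD of 1.65, 2.2 and 3.0.

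**7. If the covariate depends on arm.** With an assumed 0.3 SD arm-dependent shift in initial-plan NTCP, null rejection of the adjusted test rose to 7–16%. With a covariate independent of arm, the table in step 5 shows no inflation from adjusting.

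**The case against.** **Nothing is invalid.** This stands. Leaving out a prognostic covariate does not bias a randomised comparison, and the calculation assumed no covariates. A reader might infer that the test is biased or that 92, 98 or 120 is wrong; the documents do not support that. Nor does the word homogeneous in section 4 clash with the large dispersion. There it justifies restricting the diagnosis to the model's source population and does not claim equal lesion risk.

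**The covariate is less clean than it looks.** This stands in part. An NTCP on the conventional plan is explicit only for controls. For the experimental arm it is inferred from the reference to a second computation. Controls may be planned in each center's own system, while re-planning uses one named system. The documents do not say that NTCP is a single number per patient. The patient-level summary and the model version therefore have to be specified.

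**Adjustment could introduce bias.** This is the strongest objection, and it stands. Randomisation is at the baseline visit, and no text says the initial plan is made before allocation or blind to it; only observers are blinded. A planner who knows the plan will be redone may produce one with higher NTCP, and adjustment would then credit the excess to treatment. At an assumed rate ratio of 2.2 per SD, a 0.2 SD arm difference gives 2.2^0.2 = 1.17. That is about as large as the chance imbalance to be removed, but systematic. Locking the plan only before re-planning does not cure this, because allocation may already be known.

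**The gain is uncertain and the data are sparse.** This stands as a limit on size. The rise from 79.8% to 90.4% exceeds the likelihood-ratio simulations. About 0.128 × 49 ≈ 6 experimental patients are expected to have a lesion. In a run of 1,200 trials per row with Wald tests, the adjusted fit failed in 7% of trials at the 50% share. Counting failures as non-rejections gave 88.2% adjusted against 90.7% unadjusted. One small run of about 400 trials per row had adjusted null rejection up to 4.6%; the 2,000-trial series did not confirm this.

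**Conclusion.** The point holds as a loss of efficiency in an analysis that the protocol itself fixes. The confirmatory model adjusts for a dose that will hardly vary and for center, and omits the predictor on which the intervention is built. The cost is about 0 to 5 power points, and 8 under a strong assumed effect, plus unadjusted chance imbalance in predicted risk. If NTCP does not predict lesions, there is no gain.

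This rests on three assumptions: that initial-plan NTCP is computed in both arms (stated for controls, implied for the experimental arm), that it can be reduced to one value per patient, and that it has some predictive strength, which the documents do not quantify. A reader might infer that adding it is free and safe as the protocol stands. It is not, because nothing there makes the initial plan independent of allocation.

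**What to change.** In the synopsis and section 12.3.2, add one fixed covariate to the confirmatory model: a patient-level summary, for example the logit, of the NTCP of the initial conventional plan. Compute it with the same NTCP model and version in both arms. Add it to the imputation models too. Make the change before any unblinded interim look, since it cannot credibly be made once outcomes by arm are known.

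State the condition in sections 5.1 and 12.4.1: the initial plan and its NTCP are finalised and stored for every patient before allocation is released, or by a planner blind to allocation. If this cannot be ensured, keep the present confirmatory model and use the adjusted one only as a sensitivity analysis. Never adjust for the NTCP of the re-optimised plan, which is affected by treatment.

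The cost is a small change in the order of planning and randomisation, storage of one value per patient, and one degree of freedom. Section 5.1 already refers to an initial plan for re-planned patients, so no extra plan should be needed.
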